Study Population. Our clinical population will be men and women (N=5 to 7) 21-60 years old who are currently living with HIV (under antiretroviral therapy for 5+ years with a suppressed viral load).

Recruitment strategy. Co-I [name] has extensive experience in HIV patient recruitment and will oversee the recruitment team, during the recruitment phase, as well as the safety monitoring. Five PLWH (men and women) will be primarily recruited from The SHARC Registry (IRB# 201400073), a UF-IRB-approved registry of over 600 HIV patients who have agreed to be contacted about future research. Written informed consent will be obtained, and blood will be collected at the UF CTRB clinical research center. Inclusion criteria are: ability to read English and provide written consent; willingness to take CBD and to participate in follow up for two months; older than 21 and younger than 60; under antiretroviral therapy for 5+ years and suppressed viral load (CD4 count <350cells/ml); patients must agree to practice acceptable methods of birth control, namely sterilization (female tubal ligation or occlusion, male vasectomy), long-acting reversible contraceptives (intrauterine devices, hormonal implants), short-acting hormonal methods (pill, mini pills, patch, shot, vaginal ring), and condoms.

The main exclusion criterion will be conditions/medications that may impair the immune response (e.g. rheumatoid arthritis, cancer, diabetes chronic infections, CAD, cellulitis, autoimmune diseases such as lupus, sarcoidosis, and all medications they may affect inflammation such as aspirin, steroids, statins);), pregnancy, and current marijuana or CBD use (urine drug screen). Further exclusion criteria will be: excluding subjects taking anti-seizure medicines, with any history of seizure disorder or head trauma, any history of hepatic/liver disease or renal disease, any history of cardiovascular diseases; women who are lactating (in addition to existing exclusion criteria for pregnancy). Co-I [name] (a physician) will review conditions/medications after the initial interview before the patient is enrolled to exclude risks of drug interactions or hepatotoxicity. UF/Shands staff and students will not be considered for enrollment. Presence of chronic pain will not be considered as a necessary condition for enrollment.

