Safety Monitoring and Stopping Criteria: Safety monitoring will occur during the initial baseline visit as well as throughout the participant's duration in the study, including a 1week follow-up contact after study termination. As noted below, the baseline assessment conducted during the first visit will include a brief physical exam (including vital signs) and a thorough medical and psychiatric history, including a review of past medical history, concomitant medications, inclusion/exclusion criteria, and potential contraindications. Safety monitoring will include active and passive surveillance procedures using preexisting safety monitoring guidelines. Participants will be assessed actively at each laboratory visit by study personnel using the side effects/adverse events checklist. Each participant will be read each side effect/adverse event from the checklist and instructed to self-report as yes (go) or no (no go). If a participant experiences any of the side effects/adverse events from the checklist provided at the baseline visit, study personnel will then contact the study physician ([name]) for consultation. The side effects/adverse events will be triaged as mild, moderate or severe, and a determination will be made by the study physician as to whether the side effect/adverse event is due to the investigational test article or some other circumstance (e.g. food poisoning). If the reaction or event is determined to be due to the investigational test article and graded moderate to severe by the study physician, the participant will then be instructed to stop participation and advised to seek medical care by their primary physician or hospital. (Refer to stopping

criteria below). Any serious adverse reaction or event will be followed until full resolution. All adverse reactions and events will be reported to the UF IRB within 24-48-hrs and documented in the participant's file (redcap). The PI/physician decides that the participant should be withdrawn for **safety reasons** (presence of active lesions in the oral cavity/sublingual region or suffering side effects or adverse events associated with the use of the investigational product). List of side effects and adverse reactions are listed below*

Stopping Criteria:

- 1. Participant is unwilling to continue in the study.
- 2. Lack of compliance with protocol.
- 3. Investigator or study sponsor stops the study for any reason.

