Participants will then be instructed on how to perform their own passive surveillance for identifying these side effects/adverse events and what to do if they experience any of them between study visits while they are ingesting the investigational product. Each participant will be provided a daily log chart to record their daily CBD doses for compliance and monitoring purposes. During the passive surveillance period participants will be instructed to contact study personnel if they experience any of the side effects/adverse events from the checklist provided at the baseline visit. Study personnel will then contact the study physician ([name]) for consultation. The side effects/adverse reactions will be triaged as mild, moderate or severe, and a determination will be made as to whether the side effect/adverse reaction is due to the investigational product or some other circumstance (e.g. food poisoning). If the event is determined to be due to the investigational product and graded moderate to severe by the study physician, the participant will then be instructed to stop participation and seek medical care by their primary physician or hospital. Any participant that reports a serious adverse event will be followed to full resolution.

Patients will be contacted weekly and asked about missing doses. We will take note of any missed dose. Approximately at days 15 and 45, patients will be asked to provide a picture, sent via text to the study phone, with a close up of their CDB bottles, so that we can verify the liquid level. Patients will be instructed to not include anything identifiable in the background. Patients will be also instructed to bring their CBD bottles at every visit after the first. In case of non compliance (e.g., the patient forgets to bring the bottle or does not send the picture), the PI will consider whether to withdraw the patient for the study.

Study personnel will perform a follow-up phone call at 1 week after completion from the study for continued safety monitoring. Study personnel will refer to the checklist to determine if the participant has experienced or is experiencing any side effects or adverse events using the safety monitoring guidelines. If the participant reports experiencing any of the side effects/adverse events from the checklist the study physician will be consulted immediately for guidance and the participant's condition will be followed until full resolution.

Experimental Procedures:

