Screening: Study coordinator will screen candidate to determine if they meet the inclusion criteria for the study. The baseline visit activity will be described to the patient. The patient will sign the consent form. Instruction/demonstration about CBD and dropper use will be provided.

Visit 1: Baseline Evaluation before CBD administration

Activities during visit 1:

- Patient reads and signs the consent form.
- Patient completes a brief form providing information (e.g. age, address, phone number, etc., health history).
- Measure of patient's height, weight, and vital signs (HR, blood pressure, body temperature).
- Patient completes a urine drug test
- Patient completes a urine pregnancy test is they have the ability to become pregnant
- Patient fills questionnaires: PASS (Pain Anxiety Symptom Scale; four dimensions of pain measured: cognitive anxiety, escape/avoidance, fearful appraisal, physiological anxiety), VAS (Pain Experience Visual Analogue Scales; anxiety, depression, anger), PSQI (Pittsburg Sleep Quality Index; self-report used to assess a subject's usual quality of sleep)
- A trained nurse or technician draws a blood sample
- The patient is given 2 30mL bottles with a syringe dropper with instructions/demonstration to take the solution under the tongue (0.5 cc ~1/2 dropper) twice per day (BID), 12 hours apart (morning and evening), at the prescribed daily dosage (62.5mg/day).
- The patient schedules the next test visits to the laboratory.
- The patient receives \$100 for completing this visit.

Visit 2: Follow-up after a month period of CBD administration

Activities during visit 2 (day 26-34):

- Measure vital signs of the patient as in visit 1.
- Questionnaire filling as in visit 1.
- Blood draw as in visit 1.
- The patient schedules the next test visits to the laboratory.
- The patient receives \$100 for completing this visit.

Visit 3: Follow-up after a two-month period of CBD administration

Activities during visit 3 (day 56-64):

- Measure vital signs of the patient as in visit 1.
- Questionnaire filling as in visit 1.
- Blood draw as in visit 1.
- The patient schedules the next test visits to the laboratory.
- The patient receives \$100 for completing this visit.

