Primary Outcomes: This study takes a single-cell perspective, i.e., we will collect a large number of cells from a small number of patients, and we will measure RNA expression per single cell (not per patient). Note that from the single cell point of view, the number of patients (5-7) is sufficient to derive statistically viable results, as we will collect 5,000 cells from each patient at each time point (total 75,000-105,000 cells). Each cell will be sequence individually to read the RNA expression from a panel of approximately 20,000 genes. Cells will be pooled from all patients, and clustered via unsupervised algorithms into clusters of different cell types (e.g. T cells, B cells, monocytes). Our primary outcomes will be the extraction of gene expression patterns (RNA) from specific immune cell types found in PBMC (e.g., B cells, T cells, monocytes). We will regress these gene markers against the variation in baseline inflammation (C-reactive protein, erythrocyte sedimentation rate, and procalcitonin). After CBD administration to obtain CBD-related biomarkers for inflammation reduction. The difference in gene expression will be measured in fold change, p-value, and ratio of cell fraction expressing the marker gene. These biomarker gene will be unique for each cell type. We expect to extract specific biomarkers for each cell type and understand how CBD alters gene expressions of different immune cells in a different way-overall, we expect the genes of the MAPK signaling pathway (MAPK families play an important role in complex cellular programs like proliferation, differentiation, development, transformation, and apoptosis) to be strongly altered.

Secondary Outcomes. Self-report pain ratings will be used to determine peak pain intensity and pain persistence. The brief pain inventory (BPI) will be used to self-report pain perception. The inventory consists of rating pain on a visual analog scale (VAS). A 10cm line is drawn with 0 (no pain) on the left pole and 10 (worst pain imaginable) on the right pole. The inventory asks participants to rate their level of pain by placing a slash on the line that best represents their current level of pain as well as pain at its worst, best and average over the past 24 hours. The highest worst pain intensity reported during the intervention will be recorded as the peak pain intensity.

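### Inflammation-altering medicines and cannabis are screened out at entry but not asked about again, and no rule links intercurrent illness to the analysis, so a co-exposed on-CBD sample would be read as a CBD effect

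*Combined protocol and SAP*

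**What the plan says.** **At entry.** Under Recruitment strategy in Section 6, the main exclusion criterion covers conditions and medicines that may impair the immune response. It names "all medications they may affect inflammation such as aspirin, steroids, statins" and, among conditions, "diabetes chronic infections, CAD, cellulitis". Cannabis is excluded as "current marijuana or CBD use (urine drug screen" (the bracket closes there). A physician "will review conditions/medications after the initial interview before the patient is enrolled". Safety Monitoring and Stopping Criteria adds to the first-visit assessment "a review of past medical history, concomitant medications, inclusion/exclusion criteria, and potential contraindications". Under Experimental Procedures, the urine drug test is listed at visit 1.

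**After entry.** The lists for visit 2 (days 26-34) and visit 3 (days 56-64) contain vital signs, questionnaires, a blood draw, scheduling and payment. Between visits, "Patients will be contacted weekly and asked about missing doses"; the daily log, the bottle photographs and the bottle return also concern study doses. A side-effect checklist is read at each laboratory visit. The ten potential side effects printed in the protocol do not include a new medicine, marijuana or non-study CBD.

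**In the analysis.** CBD biomarker extraction contrasts each cell type at baseline with its counterpart on CBD and takes the difference as the effect of CBD. Primary Outcomes pools cells over patients and regresses gene markers on inflammation, measured by "C-reactive protein, erythrocyte sedimentation rate, and procalcitonin". There is no control group. No covariate, sample-exclusion rule or sensitivity analysis deals with other exposures.

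**The concern.** The plan treats these medicines and cannabis as able to distort what it measures; that is the evident reason for excluding them. The same exposure in week 4 or week 8 distorts the on-CBD sample just as it would distort the baseline sample, but nothing in the follow-up schedule asks about it.

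Such exposures are foreseeable. The Background (Section 4) says cannabinoids are widely used by people with HIV, including for chronic pain, and that CBD is on sale in grocery stores. Chronic pain is not required for entry, but it is not excluded either, so as-needed analgesic use over two months is plausible.

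The Background also reports MAPK-signalling changes in blood cells of recreational cannabis users and less chronic inflammation in users with HIV. Resumed cannabis use could therefore produce the very signature the trial wants to attribute to the study product. A steroid or aspirin course could imitate the hypothesised anti-inflammatory effect, and an infection could mask it. Regressing genes on the inflammation markers is no protection, because one such event can move genes and markers together. An exposure not recorded at the time may not be recoverable later.

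**Working it through.** **The plan's own size figure.** Patients × 3 time points × 5,000 cells: 5 × 3 × 5,000 = 75,000 and 7 × 3 × 5,000 = 105,000. Both agree with the stated range of 75,000-105,000.

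**Entry criteria beside follow-up checks**

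| Exposure | At entry | After baseline |
|---|---|---|
| Medicines affecting inflammation | Physician review; baseline medication review | No item found |
| Marijuana, non-study CBD | Urine drug screen at visit 1 | No item found |
| Illness | Listed conditions excluded (chronic infections and cellulitis among them) | Temperature at visits 2 and 3, symptom checklist, adverse event record; no link to the analysis |

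**Chance that at least one on-CBD sample is affected.** There are 2n on-CBD samples: 2 × 5 = 10 or 2 × 7 = 14. The documents give no rate, so p per sample is assumed, with samples independent. The formula is 1 − (1 − p)^(2n).

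| Assumed p | 10 samples | 14 samples |
|---|---|---|
| 2% | 1 − 0.98^10 = 18% | 1 − 0.98^14 = 25% |
| 5% | 1 − 0.95^10 = 40% | 1 − 0.95^14 = 51% |
| 20% | 1 − 0.80^10 = 89% | 1 − 0.80^14 = 96% |

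**Weight of one affected sample.** It is 1/14 to 1/10 of all on-CBD samples, or 7-10%. Within a single visit it is 1/7 to 1/5, or 14-20%.

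**Illustration of leverage in one visit's contrast with baseline.** Assume the affected patient's expression of a gene shifts by d = 0.5 SD and nobody else's changes. Treat cells as independent, in line with the plan's argument that its cell count suffices. The pooled shift is d/n and z = (d/n)/√(2/(5,000n)).

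- n = 5: 0.10/√(2/25,000) = 11.2.
- n = 7: 0.0714/√(2/35,000) = 9.4.
- For a cell type assumed to be 10% of cells (500 per sample): 0.10/√(2/2,500) = 3.5 and 0.0714/√(2/3,500) = 3.0.

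The plan states no significance level. At an assumed two-sided 5%, the cut-off is 1.96 unadjusted and 4.71 with Bonferroni adjustment for about 20,000 genes. Under these assumptions one patient alone passes both cut-offs using all cells, and only the unadjusted one in the smaller cell type.

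**The case against.** A reader might infer that illness is never checked after entry. The documents do not support that. Vital signs at visits 2 and 3 follow visit 1, which includes body temperature. The printed side effects include fatigue, gastro-intestinal distress, palpitations, shortness of breath and rash, which overlap with acute illness. A positive answer goes to the study physician, who judges whether the product or something else is the cause, and events are filed in the study database. A symptomatic illness can therefore leave a record. What is missing is a rule that uses it.

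A reader might also infer that colds or vaccination breach an exclusion. The criteria name chronic infections and cellulitis, not every acute infection, and do not mention vaccination. Asking about these is a sensible extension rather than enforcement of an existing criterion.

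The participant checklist is described as detailed, and existing safety guidelines are invoked; neither is fully visible in the text reviewed. Calls may also range wider than missed doses, since the protocol foresees suicidal thoughts being disclosed by telephone. The finding therefore rests on the printed list and the stated content of visits and contacts.

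Finally, the rates are assumed, a patient's two visits may not be independent, and an affected sample is not the same as a changed result. Some exposures imitate the effect and others hide it, so no net direction of bias is shown. This is also an uncontrolled pilot, in which even a sensitivity display cannot isolate CBD. All of this limits the claim. None of it supplies the missing question on medicines and cannabis.

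**Conclusion.** The point holds for medicines that affect inflammation and for marijuana or non-study CBD: the documents show a check at entry and none afterwards. For illness it holds in a narrower form: there is partial capture, but no rule carrying it into the analysis. Followed as written, the plan gives no planned means of identifying a sample co-exposed to such a medicine or to cannabis, and that sample would be analysed as a CBD effect.

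The size is conditional. The chance of at least one affected on-CBD sample runs from 18-25% at an assumed 2% per sample to 89-96% at 20%. That range shows how sensitive the answer is to an unknown rate; it is not an estimate of what will happen. The firm figure is that one sample is 7-10% of the on-CBD samples. The z values rest on an assumed shift and on treating cells as independent; they show that one patient could create an apparent biomarker, not that one will. The change is worth making before enrolment and does not put the pilot's feasibility in doubt.

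**What to change.** At the existing weekly contacts and before each blood draw, ask a short fixed set of self-report questions covering the time since last contact:

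- any new or as-needed medicine that may affect inflammation;
- marijuana or non-study CBD use;
- acute illness, fever or vaccination.

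Record the answers with dates. Before any sample is analysed, set a written rule for flagging samples that uses these answers together with the recorded temperature and adverse events. Report the primary gene results and the CRP, ESR and procalcitonin results with and without flagged samples, by patient.

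Do not rely on moving the draw. Two 30 mL bottles hold 60 mL, and 0.5 mL twice daily is 1 mL a day, so the supply lasts 60 days, while the visit 3 window runs to day 64. A draw postponed past day 60 may follow the end of supply and bring in a new distortion. Self-report also avoids having to interpret a repeat urine screen during hemp-extract use, which the documents do not address.

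The cost is a few extra questions at contacts that already take place, one form and one sensitivity display. With 5 to 7 patients that display will be imprecise, and it depends on honest reporting.

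### During dosing, adverse events are actively sought only at visits 2 and 3, about 30 days apart; the weekly contacts are described as covering missed doses and no adverse-event question is specified

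*Combined protocol and SAP*

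**What the plan says.** All references are to section 6 (Research Plan) of the combined protocol and SAP unless stated otherwise.

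- **Active enquiry.** Safety Monitoring and Stopping Criteria places it at the visits: "Participants will be assessed actively at each laboratory visit by study personnel using the side effects/adverse events checklist". The method is explicit: "Each participant will be read each side effect/adverse event from the checklist and instructed to self-report as yes (go) or no (no go".
- **Between visits.** The plan calls this period passive surveillance, and the participant starts the contact: "participants will be instructed to contact study personnel if they experience any of the side effects/adverse events from the checklist provided at the baseline visit". Participants receive the checklist at baseline and are instructed in what to watch for and what to do.
- **Weekly contact.** "Patients will be contacted weekly and asked about missing doses". The sentences that follow concern recording missed doses, bottle photographs at about days 15 and 45, bringing bottles to visits, and what happens on non-compliance. No adverse-event question is mentioned.
- **After completion.** "Study personnel will perform a follow-up phone call at 1 week after completion from the study for continued safety monitoring". Here the plan does say that staff will use the checklist.
- **Visit timing.** Under Experimental Procedures: "Activities during visit 2 (day 26-34") and "Activities during visit 3 (day 56-64"). The activity lists for these visits do not repeat the checklist. I take the general requirement for every laboratory visit as governing.

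**The concern.** Staff are already in touch with each participant every week, yet the plan describes that contact as an adherence check. Active safety enquiry during dosing comes about once a month.

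The plan's own safety rules depend on staff knowing of an event. Physician grading, the judgement of relatedness, the instruction to stop participation for related moderate or severe events, and IRB reporting within 24-48 hours all come after that. An event the participant does not volunteer waits for the next visit, and dosing may continue meanwhile. Its onset date is then recalled over as much as a month.

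There is also a link to adherence. A missed dose may be the first sign of a side effect. The plan records the miss but specifies no question about its cause, and lack of compliance is itself a stopping criterion. A tolerability problem could therefore be recorded as non-compliance. With 5 to 7 participants, one event missed or misclassified changes the safety picture of a pilot meant to inform a larger trial.

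**Working it through.** The plan states no figure for the interval between active enquiries, so there is nothing to reproduce. The check is a day count.

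**Inputs**
- Baseline (visit 1): taken as day 0. This is an assumption; counting it as day 1 shortens the first gap by one day.
- Visit 2: day 26 to 34. Visit 3: day 56 to 64 (Experimental Procedures).
- Dosing period: 60 days (section 5, Specific Aims). The supply agrees: two 30 mL bottles at 0.5 cc twice a day give 60 mL / 1 mL per day = 60 days.
- Participants: 5 to 7.

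**Gap from baseline to visit 2** = visit 2 day − 0
- Shortest 26 days, longest 34 days (34 / 7 = 4.9 weeks). It never exceeds five weeks.

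**Gap from visit 2 to visit 3** = visit 3 day − visit 2 day
- Nominal: 60 − 30 = 30 days (4.3 weeks).
- Shortest: 56 − 34 = 22 days. Longest: 64 − 26 = 38 days (5.4 weeks).
- The windows allow 9 × 9 = 81 pairs of visit days. The gap exceeds 35 days in 6 of them: visit 2 on day 26 with visit 3 on day 62, 63 or 64; day 27 with day 63 or 64; day 28 with day 64.

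**Part of the longest gap that falls within dosing**
- From the earliest visit 2 to the end of the planned course: 60 − 26 = 34 days. The other 38 − 34 = 4 days come after planned dosing ends.

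**Post-study checklist call**
- One week after visit 3, if that is completion: 56 + 7 = day 63 to 64 + 7 = day 71.

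**With the checklist added to the weekly contact**
- If contacts fall on days 7, 14, 21 and so on, those inside the longest gap (day 26 to 64) are days 28, 35, 42, 49, 56 and 63, which is six. The longest interval becomes 7 days.
- The plan does not say whether contacts run past day 60. If the last is day 56, the interval to a day-64 visit is 8 days, of which 60 − 56 = 4 are within dosing.
- Number of contacts: 60 / 7, rounded down, = 8 per participant; 8 × 5 = 40 to 8 × 7 = 56 in total.

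**The case against.** **The text is silent, and silence is not exclusion.** The plan does not say that missed doses are the whole content of the weekly contact. It says monitoring runs throughout participation under existing guidelines that we cannot see, it provides a response if suicidal thoughts are indicated during visits or phone calls, and a figure in this section is not shown. A reader might infer that callers are confined to missed doses; the documents do not go that far. However, more than silence supports the narrower point. The plan itself labels the between-visit period passive, keeps the weekly-contact paragraph to adherence, and names the checklist for the post-study call but not for the weekly contacts. The suicidality provision says what to do if thoughts are indicated, not that anyone asks.

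**Participants are not left unguided.** They hold the checklist and are told to report any listed event, which then goes to physician triage. This stands. An event goes unnoticed only if the participant does not follow that instruction. The documents give no rate at which this happens, so I make no claim about how many events would be missed.

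**The longest gap is a corner case.** This also stands. A reader might infer from the 38 days that someone could keep dosing through an event for more than five weeks. That gap needs an early visit 2 and a late visit 3, and on the planned course at most 34 of those days are dosing days.

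**The mode of contact is not stated.** True. The same paragraph uses text messages for bottle photographs, so it should not be assumed that staff speak to participants every week.

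**Mixed active and passive surveillance is a deliberate choice in a study the protocol regards as low risk.** It is, and nothing here is a contradiction. The question is only whether an existing contact could do more.

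**Conclusion.** The point holds as a gap in the described design. During dosing, active enquiry after baseline is planned only at visits 2 and 3, nominally 30 days apart. The windows allow 34 days to visit 2 and 38 days between visits 2 and 3, with at most 34 of the latter within the 60-day course. The ordinary 30-day gap is enough to support the recommendation; the extreme is not needed. The post-study checklist call is a further active enquiry, so the limitation applies to the dosing period and not to the whole study.

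No other layer clearly closes the gap. The daily log is described as a record of doses, and the team's monitoring meetings are quarterly, an interval longer than the course itself.

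The conclusion assumes that baseline is day 0, that the checklist is read at visits 2 and 3 as the general rule requires, and that the text describes the weekly contact fully. If staff already ask about adverse events each week, the remaining task is to write that down. I class this as a cheap improvement.

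**What to change.** In the paragraph on weekly contacts (section 6, after the passive-surveillance text), change the stated content to: *asked about missed doses and the reason for them, and asked the side effects/adverse events checklist*. State that positive answers enter the physician triage already described under Safety Monitoring and Stopping Criteria and are recorded in REDCap. State the mode of contact as well.

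No dose, grading, stopping or reporting rule changes, and no visit is added. The cost is a somewhat longer weekly contact, about 8 per participant and 40-56 in total. If the contacts are currently text messages, the checklist would have to be sent by text or asked by phone, which is a modest new procedure.

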Motivation to study single cells. The molecular and cellular changes underlying the inflammation mitigation caused by CBD-administration are largely unknown, and stand as a major challenge both for understanding its basic biology (e.g., pathways involved, molecular mechanisms) and for the urgent unmet need of reducing the long-term harm chronic inflammation causes in PLWH. Our hypothesis is that CBD alters monocyte migration capacity with MAPK-dependent alterations. We expect this alteration to have

chain-effects based on cellular cross-talk, i.e., that different PBMC cell types (such as Tcells and B-cells) might express specific CBD-induced phenotypes. We hypothesize CBD-alterations to reverberate along the whole immune-modulation system through cellular cross-talk. Given the complexity of the immune response, we deem traditional (bulk) RNA sequencing as insufficient for the task. Population-averaged genomic profiling cannot adequately unravel the inter-cellular regulation in situ. This study will leverage the efficiency of newly available single-cell technologies to create a powerful dataset unveiling the functional properties of thousands of individual cells.

Sample collection and processing. We plan to collect samples from five to seven patients over three time points: baseline (no CBD), and after one and two months of CBD-administration with 5,000 cells sequenced per sample. Five to seven patients (15 to 21 samples) will provide the transcriptomes of 75,000-105,000 single cells, a large dataset for scRNAseq. Immediately after collection, samples will be collected by TBD Lab technician to be processed for scRNAseq at UF ICBR (PBMC scRNAseq experiments are routinely run at ICBR).

Data analysis. During the post-processing period, single-cell reads (count matrices) will be filtered for quality control. Unsupervised clustering will isolate statistically robust populations of similar cells. Clusters will be visualized using Principal Component Analysis (PCA), t-Distributed Stochastic Neighbor Embedding (tSNE), and Uniform Manifold Approximation and Projection (UMAP). The most informative gene expression markers will be identified by a host of non-parametric tests (e.g., the Kolmogorov–Smirnov test), comparing a given cluster against either a nearby cluster or all other clusters. Clusters of cells will be annotated by using their marker genes/pathways⁻ and prior biological knowledge to characterize each sample's cell composition.

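### A forgotten bottle or unsent photo can lead to withdrawal at the PI's discretion, with no missed-dose criterion and no provision for later outcome samples, in a study of 5 to 7 patients

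*Combined protocol and SAP*

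**What the plan says.** All of this is in section 6, Research Plan.

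- **Adherence checks.** "Approximately at days 15 and 45, patients will be asked to provide a picture" of the bottles, and they are to "bring their CBD bottles at every visit after the first". That makes four checks per patient: day 15, visit 2 (day 26–34), day 45 and visit 3 (day 56–64).
- **Consequence of a missed check.** An unsent photo and a forgotten bottle are the named examples of non-compliance, and on either one "the PI will consider whether to withdraw the patient for the study". No number or share of missed doses is set. Non-compliance also appears among the Stopping Criteria, again unquantified.
- **Other adherence data.** Patients keep a daily dose log and are asked every week about missed doses.
- **Adverse events.** If an event is judged due to the product and "graded moderate to severe by the study physician, the participant will then be instructed to stop participation".
- **Serious suicidality.** The patient is asked to stop CBD, and the study continues to follow a patient whom it has referred. The content of that follow-up is not defined.
- **Sample and analysis.** "We plan to collect samples from five to seven patients over three time points". Under Primary Outcomes, cells from all patients are pooled. Under CBD biomarker extraction, baseline clusters are contrasted with their post-CBD counterparts. No analysis set, replacement rule or missing-data rule is given.

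**The concern.** An unsent photo means that adherence was not verified on that occasion. It does not show that doses were missed, and the dose log and weekly contacts may show the opposite. Yet it is a named ground for considering removal of a dosed patient, decided without a stated criterion by an investigator who knows that the patient is on CBD.

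Nothing provides for visit 2 or 3 blood and questionnaires after withdrawal. If a patient leaves before visit 2, the pooled baseline cells may include that person while the post-CBD cells do not. The baseline versus post-CBD contrast would then mix change on CBD with a change in who contributes cells. With 5 to 7 patients, one such loss matters.

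The adverse-event wording raises a narrower question: whether stopping participation means stopping CBD or also ending outcome collection. The event checklist includes anxiety, low mood and insomnia. The questionnaires measure anxiety, depression and sleep, so the answer affects the secondary outcomes.

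**Working it through.** **The plan's own figure.** "we will collect 5,000 cells from each patient at each time point (total 75,000-105,000 cells"). 5 × 3 × 5,000 = 75,000 and 7 × 3 × 5,000 = 105,000. Both reproduce, but only if every patient gives all three samples.

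**One withdrawal before visit 2.**
- Share of patients lost from the post-CBD data: 1/5 = 20%, or 1/7 = 14%.
- Cells remaining: (15 − 2) × 5,000 = 65,000, or (21 − 2) × 5,000 = 95,000.
- At N=5, pooling everything collected gives 5 × 5,000 = 25,000 baseline cells from five people and 4 × 2 × 5,000 = 40,000 post-CBD cells from four.

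**Which checks can cost a sample.** The visit 3 check falls at the last planned sampling visit, so no later visit can be lost. Three remain: day 15 (before all post-CBD data), visit 2 (coincides with the first post-CBD sample) and day 45 (before visit 3 only).

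**Chance of triggering the clause.** The documents give no miss rate. Assume a probability q of 5% to 10% per check, independent between checks and patients.

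| Quantity | Formula | q = 5% | q = 10% |
|---|---|---|---|
| One patient misses at least one of three checks | 1 − (1−q)^3 | 14% | 27% |
| At least one patient does so, N=5 | 1 − (1−q)^15 | 54% | 79% |
| At least one patient does so, N=7 | 1 − (1−q)^21 | 66% | 89% |
| At least one misses the day-15 check, N=5 | 1 − (1−q)^5 | 23% | 41% |
| At least one misses the day-15 check, N=7 | 1 − (1−q)^7 | 30% | 52% |

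These are chances that the clause comes into play. The chance of actual withdrawal is lower by an unknown factor, because the PI decides.

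**Off-drug samples.** The Investigational Product text gives a half-life of 18–32 hours. Five half-lives are 90–160 hours, about 4 to 7 days. Blood drawn weeks after stopping CBD is therefore off-drug.

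**The case against.** The strongest reply is that the clause only asks the PI to consider withdrawal, and that the PI has the dose log and weekly contacts to judge by. At day 15 no post-CBD sample exists, so the PI cannot be choosing patients on their post-CBD expression results. A patient withdrawn at day 45 should already have baseline and month-1 data. An on-treatment contrast is also a defensible choice for a mechanistic pilot. All of this stands. It limits the size of the problem, but it does not supply the missing criterion or any provision for later samples.

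A reader might infer more than the documents support:

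- **That withdrawal ends all data collection.** This is not stated. Serious events are followed to resolution, and a safety call follows one week after completion. What is missing is provision for further outcome data.
- **That only completers are analysed.** No analysis set is defined, and samples taken before withdrawal could still be pooled.
- **That tolerability will be overstated.** Adverse events are reported to the IRB and documented in the participant's file, and nothing says that tolerability is estimated from those who stay.
- **That losing a patient raises a p-value floor.** The plan specifies no patient-level exact test.

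**Conclusion.** The concern holds in limited form. The plan allows a dosed patient to be removed over a missing measurement, without a criterion, and does not say whether outcome samples are still sought. One loss before visit 2 takes 14–20% of patients out of the post-CBD data and can unbalance the pooled contrast.

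The exposure figures rest on an assumed 5–10% miss rate and on independence. If misses cluster completely within the same patients, per-patient exposure falls to 5–10%, and the chance that anyone is exposed falls to the day-15 rows of the table. The direction of any resulting bias cannot be fixed from the documents.

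The adverse-event part reduces to an inconsistency. One passage stops participation, while another stops CBD and continues follow-up. The investigators need to reconcile them, and no clinical stopping rule is implied here.

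**What to change.** 1. **Compliance text in section 6.** State that a missed photo or bottle is re-requested and recorded as *adherence unverified*, and does not by itself end the visit 2 and 3 blood draws and questionnaires.
2. **Analysis.** Make the baseline versus post-CBD contrast within patients who have both samples. Include those with unverified adherence, and report a verified-adherent analysis as support.
3. **Stopping text in section 6.** Reconcile the stop-participation wording with the suicidality text, and say whether outcome data are still sought from willing participants after CBD stops. Flag any off-drug samples and keep them apart from the on-treatment contrast.

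The cost is a few sentences of protocol wording and possibly a few extra visits. The downside is some dilution if patients with unverified adherence did miss doses, which the supportive analysis would help to show.
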